9.2. Setting

The study population will include US patients with SCD between the ages of 12 and 85 years who are enrolled in a health insurance plan (commercial, Medicare, Medicaid) continuously during the 365 days prior to and including the index date (baseline) and 180 days post-index. The index selection period is November 25, 2019 (date of Food and Drug Administration [FDA] accelerated approval for voxelotor) through January 31, 2023. The exposed group will include patients with a new prescription claim for voxelotor (no prior use 365 days prior to index date), while the control group will include matched patients who do not have a prescription claim for voxelotor. Non-voxelotor controls will include those receiving no SCD-modifying therapies as well as those receiving non-voxelotor SCD treatments to be reflective of clinical practice. Patients who have a history of stroke will be excluded from this analysis. Both the exposed and control groups may be treated with other SOC treatments such as HU and have 2 or more documented RBC transfusions prior to study index.

Depending on the source of information, approximately 50% of individuals with SCD in the US have received a RBC transfusion, and approximately 20% have received a transfusion in the past year. ¹⁶ In the feasibility assessment of Komodo Healthcare Map (KHM) dataset, race/ethnicity was documented for 90% (n=2230/2486) of patients with 87% (n=1929/2230) identifying as Black or African American. The Centers for Disease Control and Prevention (CDC) estimates 90% of individuals with SCD in the US are non-Hispanic Black or African American. ¹⁷ Socioeconomic status also plays an important factor in impacting patient behavior and access to care. While the KHM dataset does not have direct measures of patients' socioeconomic status, important indicators will be leveraged in the analysis for patients including geography by region, health insurance type, and whether a hematologist is involved in the patient's care. KHM is nationally representative of individuals with SCD. In the Komodo data, approximately 68% of patients have Medicaid as their primary insurance type.

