9.2.2. Exclusion Criteria

Table 3. Summary of Exclusion Criteria

Exclusion Criteria	Assessment Period	Operational Definition	Rationale/Validated Source
Stroke or history of stroke	[Baseline]	At least one medical claim with an ICD-10- CM diagnosis code with evidence of stroke.	This study is intended to be generalizable to SCD patients. Patients with a history of stroke may rely on RBC transfusions for disease management and will therefore be excluded.
Pregnancy	[Baseline]	At least one medical claim with an ICD-10- CM diagnosis code with evidence of pregnancy	This study is intended to be generalizable to SCD patients and this is a common exclusion for RCTs. Individuals with SCD may receive RBC transfusions to ensure adequate oxygenation of the fetus during pregnancy. Voxelotor is not indicated during pregnancy.
Hemodialysis or history of hemodialysis	[Baseline]	At least one medical claim with an ICD-10- PCS procedure code with evidence of hemodialysis.	Patients with a history of hemodialysis may rely on RBC transfusions for disease management and will therefore be excluded.
Hematopoietic stem cell transplantation (HSCT) or gene therapy or history of HSCT or gene therapy	[Baseline]	At least one medical claim with an ICD-10-PCS procedure code with evidence of HSCT or gene therapy.	Patients with a history of HSCT may rely on RBC transfusions for disease management and will therefore be excluded. After HSCT or gene therapy, their disease may be markedly improved.

Renal transplant or history of renal transplant	[Baseline]	At least one medical claim with an ICD-10- PCS procedure code with evidence of renal transplant.	Patients with a history of renal transplants may rely on RBC transfusions for disease management and will therefore be excluded.
Liver transplant or history of liver transplant	[Baseline]	At least one medical claim with an ICD-10-PCS procedure code with evidence of liver transplant.	This study is intended to be generalizable to SCD patients. Patients with a history of liver transplants may rely on RBC transfusions for disease management and will therefore be excluded.
Iron overload - Exploratory Objective 3 Subgroup Only	[Baseline]	At least one medical claim with an ICD-10- CM diagnosis code with evidence of iron overload	To assess incident events in follow-up for Exploratory Objective 3

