The results from this validation study inform the accuracy of claims data based on procedure codes in measuring RBC transfusions as an endpoint. The validation study included 13,327 patients with a documented diagnosis of SCD and at least one RBC transfusion documented in claims or EHR within the Optum Market Clarity database between January 2016 and March 2023. Among these patients, there were 46,381 RBC transfusions performed over the study period. The vast majority (91%) of these transfusions were documented in claims (42,106) with some (22%) overlap in EHR (10,394). A minority (9%) of RBC transfusions were only documented in EHR (4,275). Given these results, we believe that claims are the more reliable data source and will be used primarily for this study.

Komodo

KHM is a real-world dataset that integrates disparate sources of patient-level data to map longitudinal patient journeys. Komodo pulls de-identified, patient-level claims data from clearinghouses, payers (150+ payers including Medicare and Medicaid), and provider data

sources to follow patients as they move through the healthcare system. The patient-centric database includes both open and closed claims data and is enriched with data from EHR and other sources. Komodo's closed dataset (payer complete dataset) will be used for this analysis. Data will be included from November 25, 2018, to January 2024. The database covers all the US census regions. The all-payer claims data is fully adjudicated. Komodo is a patient-centered claims dataset that complies with the Health Insurance Portability and Accountability Act. The KHM data dictionary is included as a standalone document to this protocol.

Claritas

Claritas Rx captures patient-level data from channel partners such as specialty pharmacies, patient services hubs (including patient assistance programs), specialty distributors, claims data providers, labs and other patient services providers to enable insights into the market and patient journey. This data source contains proprietary voxelotor claims and is linked to KHM.

Quest

Quest laboratory database contains over 56 billion laboratory test results nationwide. For this study, Quest data will be linked to the KHM from November 25, 2018, through the end of data (July 31, 2024). Important baseline variables like Hb will be captured from lab data.

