For sensitivity analysis, transformations of the outcome may also be considered as appropriate. The outcome data will only be viewed overall prior to selecting a method of regression. 95% CI will be reported for the difference between the groups. Full details will be provided in the SAP.

Exploratory Objective 1 – SCD-related Complications Exploratory Objective 1.1 – Change in SCD-related Complications PPPY

VOCs, ACS, ACS + pneumonia, and priapism will be assessed as the change in the rate of events PPPY from baseline to follow-up. For each individual, the rate of each clinical outcome will be calculated as the number of events divided by the number of person-days. The change will be calculated as:

$$Change = \left(\frac{Number\ of\ events\ in\ follow-up}{Available\ days\ of\ follow-up} - \frac{Number\ of\ events\ in\ baseline}{365\ days\ *}\right)x\ 365$$
*All patients have 365 days of baseline data

The change in number of events PPPY will be analyzed using GLM with an identity link to estimate the difference in clinical outcome change rates between the two groups. If any preindex covariates that are found to be unbalanced after the PS method, it will be included in the regression as a covariate. The rate change and its 95% CI will be reported.

Exploratory Objective 1.2 – Time to Stroke

Stroke will be assessed as a time-to-event outcome. Cox proportional hazards (PH) models will be used to calculate the hazard ratio (HR); 95% CIs will be calculated using a robust variance estimator.

Exploratory Objective 2, Endpoint 1 – Number of RBC Transfusions PPPY in Follow-Up

The number of RBC transfusions that occur during the follow-up period will be assessed PPPY during available follow-up within each group. The mean number of RBC transfusions PPPY will be reported for each group. The mean difference between the groups will be assessed using a GLM similar to the primary analysis. The 95% CI will be reported for the difference between the groups.

Exploratory Objective 2, Endpoint 2 – Proportion of Patients with > 30% Reduction in RBC Transfusions

^{*}All patients have 365 days of baseline data

This outcome will be defined as the proportion of patients with a percent reduction in RBC transfusions between baseline and follow-up that is greater than 30%. For each patient, the percent change will be calculated as follows:

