9.9. Strengths and limitations of the research methods

There are some distinct differences between RWE and RCT settings. RWD allows for more generalizable patient populations, but there is less standardization and higher potential for missing values for important patient characteristics (e.g., Hb levels, SCD genotype, comorbidity scores, etc.). Additionally, in an RCT environment, healthcare interactions are on a protocolized schedule for enrolled patients. In RWD, differences exist in how often a patient sees a provider and the type of provider both across groups and within groups, which is why both of these elements will be important for PS modeling. RWD allows for less restrictive inclusion/exclusion criteria and will allow for patients with more severe SCD to be evaluated; for example, all individuals with SCD and recent history of RBC transfusion are excluded from voxelotor clinical trials as well as other medications in development for SCD.

Although there are many benefits to utilizing RWD, there are some inherent limitations. Claims data sources are subject to potential misclassification of the outcome, exposure, or covariates in observational studies (i.e., the presence of a diagnosis code on a medical claim or a generic medication on a prescription claim does not indicate the presence of disease or compliance to treatment given rule out diagnosis or coding errors). 44 The extent of miscoding is believed to be small, as study variables are drawn directly from medical claims that are used for clinical documentation and insurance reimbursement. 44 Additionally, as determined through exploratory analyses, a small proportion of patients have available lab data after linking across all three data sources; Hb will also be excluded from the PS model but will have a separate subgroup analysis because it may be an important confounder in this study. Patients will be excluded from the analysis if they have evidence of stroke in baseline so that patients receiving chronic transfusions for secondary stroke prevention are not included in the analysis. Although patients may also receive transfusions for primary stroke prevention, claims data will not have information on transcranial doppler velocity, and thus such patients will not be identifiable. However, this is estimated to be a small portion of patients within the study (less than 5% of pediatric patients with SCD receive chronic transfusions). 45

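### Exclusions for a history of stroke, hemodialysis, HSCT/gene therapy or transplant are assessed only in the 365 days before index, so the Section 9.9 assurance on secondary stroke prevention is not delivered

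*Protocol*

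**What the plan says.** Section 9.2 sets no time limit on the stroke exclusion: "Patients who have a history of stroke will be excluded from this analysis". Table 3 in Section 9.2.2 labels five exclusions as the condition or a history of it: stroke, hemodialysis, HSCT or gene therapy, renal transplant and liver transplant. Its reasons also speak of history. For stroke it says "Patients with a history of stroke may rely on RBC transfusions for disease management and will therefore be excluded", and for renal transplant "Patients with a history of renal transplants may rely on RBC transfusions for disease management and will therefore be excluded".

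The assessment period for all five is Baseline. Section 9.2 requires enrollment "continuously during the 365 days prior to and including the index date (baseline) and 180 days post-index", and the note to the formulas in Section 9.7.3 says "All patients have 365 days of baseline data". Stroke needs one claim with an ICD-10-CM diagnosis code. The other four need an ICD-10-PCS procedure code.

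Section 9.9 restates the stroke rule: "Patients will be excluded from the analysis if they have evidence of stroke in baseline". It then gives the result as "so that patients receiving chronic transfusions for secondary stroke prevention are not included in the analysis". The only residual group it concedes is patients transfused for primary stroke prevention.

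**The concern.** A promise about history is implemented by a one-year window. Section 7 describes chronic transfusion as usually monthly and recommended for stroke prevention. Such a patient easily meets the entry criterion of at least two baseline transfusions, so if the stroke exclusion misses the patient, nothing else in the criteria is aimed at removing them.

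At stake is whether the cohort is the one described. If recipients of scheduled transfusion stay in, part of the cohort has a transfusion count set by a prevention program, which is the group the protocol says it has removed. Section 9.9 would then misstate the limitation as well as leave it unmanaged.

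**Working it through.** **1. The window.** The Abstract, Section 9.2, Figure 1 and Section 9.7.3 all give a 365-day baseline. No section gives a longer look-back for any exclusion.

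**2. Data that could be used.** Section 9.4 says of the claims: "Data will be included from November 25, 2018, to January 2024". Index dates run from 25 November 2019 to 31 January 2023 (Section 9.5).

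- Earliest index: 25 Nov 2018 to 25 Nov 2019 = 365 days.
- Latest index: 25 Nov 2018 to 31 Jan 2023 = 1,528 days.
- Unused at the latest index: 1,528 − 365 = 1,163 days.

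These are calendar ceilings. Only 365 days of prior enrollment are required, so the usable history is shorter for many patients.

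**3. Cases traced through Table 3.**

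- *Stroke two years before index, monthly transfusion since.* About 12 baseline transfusions meet the inclusion criterion. The patient is excluded only if a listed stroke code appears on some claim in the last year.
- *HSCT or organ transplant two years before index.* The procedure was done once, so no procedure code falls inside the window. As defined, the history cannot be seen.
- *Hemodialysis.* It is repeated, so current dialysis is caught. Past dialysis that has stopped is not.

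**4. Effect on the primary endpoint.** Section 9.7.3 defines the change as (follow-up count / follow-up days − baseline count / 365) × 365. A stable monthly recipient gives 12 − 12 = 0 per year. Such a patient adds no spurious difference but also cannot show a reduction.

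**5. Power.** Inputs from Section 9.5: 185 treated, 370 controls, difference 1, SD 3.0, factor 1.65; two-sided 5% assumed.

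The plan's own figure first: treated n = (1 + 1/2) × (3.0 × 2.802 / 1)² × 1.65 = 175, against 185 stated. The standard error at 185/370 is 3.0 × √1.65 × √(1/185 + 1/370) = 0.347. Power is Φ(1/0.347 − 1.960) = 82.2%, against 80% stated. The planned size is slightly larger than needed.

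Now assume that a share p of both arms cannot change and that the SD stays at 3.0. The difference becomes 1 − p:

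| p (assumed) | Difference | Power at 185/370 |
|---|---|---|
| 0 | 1.00 | 82.2% |
| 2% | 0.98 | 80.6% |
| 5% | 0.95 | 78.2% |
| 10% | 0.90 | 73.7% |
| 20% | 0.80 | 63.5% |

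The documents give no value for p.

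**The case against.** Five arguments deserve weight.

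- *Code lists.* Stroke is found by diagnosis codes, and the lists are left to the SAP. If they include history or sequela codes, a patient seen monthly has many claims on which one could appear. This stands: it limits the size of the stroke leak, but it does not lengthen the window or make the assurance certain.
- *Code types.* Section 9.3 says medical history may use diagnosis, procedure and HCPCS codes. Table 2 names only ICD-10-PCS for transfusion, while Annex Table 2 also lists CPT and HCPCS. The procedure-only wording in Table 3 may therefore be shorthand. That is possible, but the wording should then be corrected.
- *Mitigation.* The baseline transfusion count is a candidate propensity-score covariate, and Table 7 stratifies by it. This stands in part: it balances how often patients are transfused, but not why.
- *Equal observability.* A fixed window treats every patient alike, whereas a longer look-back varies with enrollment. This is a fair reason to choose 365 days, but not to describe the result as excluding any history.
- *Open wording.* Section 9.9 does say that the evidence is sought in baseline. It does, but the conclusion it draws goes further than that.

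A reader might also infer that old strokes re-coded in follow-up will count as new events under exploratory objective 1.2. The documents do not establish this. It depends on the SAP code list, and the text at hand shows no legible stroke definition that would settle it. Nor should a reader set 12 transfusions a year against the planning SD of 3.0: the first is a level, the second the SD of a change.

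**Conclusion.** The point holds as a contradiction within the protocol. Sections 9.2 and 9.2.2 exclude on history, the rule looks back 365 days, and Section 9.9 claims a result that this rule does not secure. It is clearest for HSCT and transplants, weaker for stroke, and weakest for dialysis.

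The number of patients affected is unknown. The likely effect on the primary endpoint is modest dilution toward no difference: about 2 to 4 points of power if the share is 2% to 5%, and more only if it is well above that. This assumes equal shares in both arms, no change in these patients and an unchanged SD. The documents do not support a claim of large bias. The finding also rests on Baseline meaning 365 days. Table 1 was not in the text available, but every section that defines the period agrees.

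**What to change.** - In Table 3, change the assessment period for the five exclusions from Baseline to all available claims up to and including index, with a minimum of 365 days. The calendar maximum is 1,528 days, less where enrollment is shorter.
- Let the hemodialysis, HSCT/gene therapy and transplant definitions include diagnosis codes for status or history. State that these codes serve pre-index exclusion, because Section 9.7.3 also ends follow-up at exclusion events.
- Apply the same no-prior-stroke look-back to objective 1.2.
- Reword Section 9.9 to state the remaining limit: the earliest index dates gain no look-back, so some older strokes will still be missed.

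The minimum alternative is to relabel the criteria as evidence in the prior 365 days and withdraw the Section 9.9 assurance.

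The cost is a wording change and a re-run of cohort selection on claims already within the study's data period. The downside is a small loss of patients and a look-back that varies with index date and prior enrollment. Calendar-date matching balances the first but not the second. The fixed 365-day window can be kept as a sensitivity analysis.
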